8.4 Criteria for Termination of an Individual Subject

An individual subject may be terminated from the trial for any reason including, but not limited to the following:

- Subject withdrawing consent to continue in the trial
- Occurrence of an AE which precludes subsequent participation
- Requirement of an ocular surgery or intervention that is exclusionary for the trial
- Physician discretion based on the ability of the subject to continue schedule or treatment regimens according to protocol, or for the safety of the subject
- In the event that a woman becomes pregnant while participating on the study, she will be withdrawn from the study

8.5 Criteria for Termination of the Trial

The trial may be discontinued by Parion Sciences, Inc. or at the recommendation of the principal investigator after consultation with Parion. This may be based on a significant number of AEs of a similar nature that warrant such action, or at the request of Parion Sciences, Inc. Should this be necessary, both parties will arrange discontinuation procedures and notify the appropriate regulatory authority(ies) and Institutional Review Board (IRB). In terminating the study, Parion Sciences and the investigator will assure that adequate consideration is given to the protection of the subjects' interests.

8.6 Procedure for Accounting for Missing, Unused, or Spurious Data

All analyses will be based on observed data only. No attempts will be made to impute or estimate missing data.

8.7 Procedure for Reporting Deviations from the Statistical Plan

Any deviations from the statistical plan will be described and a justification given in the final clinical report.

8.8 Subjects to be Included in the Analysis

All safety analyses will include all subjects who were randomized and received at least one dose of study medication.

9 ASSESSMENT OF PHARMACODYNAMICS

Detailed measurements of tear volume before and after dose administration will be obtained using UHR-OCT (tear volume and tear meniscus height) and Keratograph 5M (tear meniscus height). Procedures for these measurements are located in [Appendix X](#).

10 ASSESSMENT OF SAFETY

10.1 Safety Parameters

Subject safety will be evaluated by a medical professional during the study. Tolerance of study medication as well as general subject well-being will be assessed. Subjects may be discontinued from the study at any time by the investigator if this action is considered in the subject's best interest.

Post dose safety parameters are measured as described in [Appendix I](#) and include:

- Assessment of adverse events ([Appendix II](#))
- Biomicroscopy and external eye examination ([Appendix IV](#))
- Assessment of comfort in taking the medication will be conducted ([Appendix XI](#))

10.2 Procedures for Adverse Events Reporting

An AE is any untoward medical occurrence in a subject or clinical investigation subject administered a pharmaceutical product, which does not necessarily have to have a causal relationship with this treatment. AEs will be documented upon signing the informed consent. A treatment emergent AE (TEAE) is an AE that either commenced following initiation of study treatment or was present prior to study treatment but increased in frequency or severity following initiation of study treatment.

A non-serious AE is any AE that does not meet the definitions for SAEs as described in [Section 10.3](#).

AEs that occur prior to subject randomization at Visit 2 will be documented in source documents. TEAEs will be monitored throughout the study and will be recorded on the CRF with the date and time of onset, date and time of resolution, intensity, seriousness, causality (relationship to study medication), treatment required and the outcome.

If an AE occurs, the investigator will institute support and/or treatment as deemed appropriate. If a non-serious AE is unresolved at the time of the last visit, a reasonable effort will be made to follow up until the AE is resolved or stabilized, the subject is lost to follow-up, or there is some other resolution of the event.

To elicit AEs simple questions with minimal connotations should be used as the initial questions at all evaluation points during the trial. For example:

- How have you felt since your last assessment?
- Have you had any health problems since your last assessment?

10.3 Serious Adverse Event Reporting

An SAE is any untoward medical occurrence occurring on this trial that results in any of the following outcomes:

- Death

- A life-threatening adverse drug experience (i.e., the subject is at immediate risk of death at the time of the event)
- In-patient hospitalization or prolongation of existing hospitalization
- A persistent or significant incapacity or substantial disruption of the ability to conduct normal life functions
- A congenital anomaly/birth defect
- Important medical events that may not result in death, be life-threatening, or require hospitalization may be considered serious when, based upon appropriate medical judgment, they may jeopardize the subject and may require medical or surgical intervention to prevent one of the outcomes listed in this definition

The Investigator or other study personnel must immediately inform Parion Sciences or designee by phone or email of any AE considered serious or otherwise significant, as described above. **In addition, a completed SAE report form must be submitted to Parion within 24 hours of initial awareness of the event.**

SAE Reporting

Dedicated Safety Email Address: [contact]

It is the responsibility of the investigator or their designee to report any event of this nature to Parion Sciences, Inc. within 24 hours of the event being brought to the investigator's or their staffs' attention. It is also the responsibility of the investigator to report all SAEs to their IRB according to their requirements and provide a copy of this notification to Parion Sciences. The investigator should make every attempt to follow all SAEs to resolution.

Information to submit when reporting an SAE to Parion Sciences, Inc. is located in [Appendix II](#).

10.4 Procedures for Reporting Pregnancy

Any subject found to be pregnant at any time during the study will be withdrawn from the study immediately. Any pregnancy outcome that meets the criteria for an SAE will be reported as an SAE. All pregnancies will be reported to Parion Sciences within 24 hours of the event being brought to the investigator's or their staffs' attention. It is also the responsibility of the investigator to report all pregnancies to their IRB according to their requirements and provide a copy of this notification to Parion Sciences. The investigator should make every attempt to follow all pregnancies to resolution (i.e., birth or voluntary or spontaneous termination of the pregnancy).

11 DIRECT ACCESS TO SOURCE DATA and DOCUMENTS

The principal investigator will permit trial-related monitoring, audits, IRB review, and regulatory inspection(s) by providing direct access to source data and documents.

12 QUALITY CONTROL AND QUALITY ASSURANCE

The progress of the study will be monitored by on-site, written, e-mail and telephone communications between personnel at the study center and Parion Sciences, Inc. (or designated monitor). The investigator will allow Parion Sciences, Inc. clinical monitors, designees, auditors, and regulatory authorities to inspect all CRFs; subject records (source documents), signed informed consent forms; records of study medication receipt, storage, and dispensation; and regulatory files related to this study.

At the time of database lock, the clinical database will be audited in order to ensure accuracy of all data as well as to provide an estimated error rate for the final, locked database. The results of the audit will be provided in the final study report. The audit will involve a comparison of CRF values with values from data listings generated from the clinical database. Values of all variables will be confirmed for the five randomly selected subjects. If the database fails to meet an accuracy rate of 99.5% (less than 1 error / 200 fields), a second set of 5 subjects will be selected. If a combined sample fails to meet an accuracy rate of 99.5%, the remainder of the database will be rechecked or take other action taken agreed with by Parion.

13 ETHICS

This protocol is written in accordance with the principles established by the 18th World Medical Assembly General Assembly (Helsinki, 1964) and amendments and clarifications adopted by subsequent General Assemblies. The investigator will make sure that the study described in this protocol is conducted in full conformance with those principles, the protocol, current FDA regulations, ICH Good Clinical Practices (GCP) guidelines, Good Laboratory Practices (GLP) guidelines, local ethical and regulatory requirements, including the Federal Food, Drug and Cosmetic Act, U.S. applicable Code of Federal Regulations (CFR) (title 21), any Ethics Committee (EC) requirements relative to clinical studies. As required by the US FDA, the study drug may not be shipped to any participating investigator until the requisite study documentation has been submitted to the IND.

13.1 Institutional Review Board

The EC/IRB must be a properly constituted board or committee operating in accordance with 21 CFR Part 56, "Institutional Review Boards." This protocol, any protocol amendments and the associated informed consent forms and translations must be submitted to the EC/IRB for review and approved before the enrollment of any subject into the trial.

All subject recruitment materials and advertising information, including translated versions of these documents, must be submitted to Parion or its designee and to the EC/IRB for review and approval prior to implementation. EC/IRB approval of any protocol amendments must be received before any of the changes outlined in the amendments are put into effect, except when the amendment has been enacted to eliminate a potential hazard to study subjects. In such cases, the chair of the EC/IRB should be notified immediately and the amendment forwarded to the EC/IRB for review and approval.

In addition, the Clinical Investigator Brochure should be submitted to the IRB.

Written IRB approval must adequately identify the materials approved. Copies of all approved materials, all correspondence with the IRB, and written approval from the IRB must be made available to Parion Sciences, Inc. (or designated monitor) *prior* to shipment of study medication and the start of subject enrollment into the study.

SAEs will be reported to the IRB by the principal investigator as required by the IRB.

13.2 Informed Consent Requirements

Written informed consent will be obtained from each subject prior to any study related procedures being performed. A copy of the signed and dated consent document will be given to each subject. The original signed and dated informed consent document must be maintained in the study files at the investigative site and be available for Parion Sciences, Inc. or designee, and regulatory authorities for review.

Each informed consent form will contain contact information with a telephone number the subject should contact if they have medical concerns 24-hours a day.

13.3 Data Handling and Record Keeping

All procedures for the handling and analysis of data will be conducted using good clinical practices meeting ICH and U.S. Food and Drug Administration (FDA) guidelines for the handling and analysis of data for clinical trials.

13.4 Data Quality Control and Reporting

After data have been entered into the study database, a system of computerized data validation checks and manual data reviews will be implemented and applied to the database. Query reports pertaining to data omissions and discrepancies will be forwarded to the clinical investigator and monitor(s) for resolution. The study database will be updated in accordance with the resolved query reports. All changes to the study database will be documented.

CRFs will be provided by Parion Sciences, Inc. All data relating to the trial must be recorded in the CRFs. The Investigator must verify that all data entries in the CRFs are accurate and complete. The CRF must be signed and dated by the Investigator upon subject withdrawal or completion of the study.

During monitoring visits, CRFs will be reviewed by study monitor(s) for completeness, accuracy, and legibility. CRFs will be compared with the source documents to ensure that there are no discrepancies. All CRF entries, corrections, and alterations must be made by an Investigator or his/her designee. Corrections must be made in such a way that the original entry is not obliterated. Correction fluid must NOT be used. The correct data must be inserted, dated and initialed by the Investigator or his/her designee. The study monitor is not allowed to make entries on the CRF pages.

The original CRF page will be retrieved by the monitor and returned to Parion Sciences, Inc. after complete review of the case. A copy must be maintained by the Investigator. If documented corrections to a CRF are needed after removal of the original CRF copy from the center, a Data Correction Form (DCF) will be used. The Investigator or a staff member must verify, sign, and date each DCF.

A log will be maintained at the sites for those subjects that do not meet eligibility criteria. Minimally this log will include the subject's age, sex and race and the reason that they were not eligible. Screen failure data will not be collected in the clinical database.

13.5 Records Retention

The study center will retain all records related to the study in compliance with ICH Good Clinical Practices Guidelines.

13.6 Publication Policy

The institution and investigators participating in this trial shall have no rights to publish, disclose or present the results of this study without prior written consent of Parion Sciences, Inc.

APPENDIX I: SCHEDULE OF VISITS AND PROCEDURES.

Table 1 Schedule of Visits and Procedures

Event	Visit 1	Visit 2		Visit 3	ET
	Screening Visit	First Treatment Visit (3 to 9 days after Visit 1)	Wash-out (7 to 14 Days)	Second Treatment Visit (7 to 14 days after Visit 2)	Early Termination Visit
Informed Consent	X ^a				
Eligibility Criteria Reviewed	X	X		X	
Medical History/Changes	X	X		X	X
Concomitant Medication/Changes	X ^b	X		X	X
Abbreviated Physical Exam	X				X
Vital Signs	X	X ^c		X ^c	X
Tear Osmolarity	X				
Assessment of Meibomian Glands ^d	X				
Pregnancy Test	X				
Serum Chemistry	X				
Hematology	X				
Dry Eye Symptoms ^e	X	X		X	
Study Medication Administration	N/A	One drop per eye in AM ^f		One drop per eye in AM ^f	
UHR-OCT Assessments ^g	X ^g	X ⁱ		X ⁱ	
Keratograph 5M	X ^g	X ⁱ		X ⁱ	
Drop Instillation Comfort Assessment ⁱ		X		X	

Event	Visit 1	Visit 2		Visit 3	ET
	Screening Visit	First Treatment Visit (3 to 9 days after Visit 1)	Wash-out (7 to 14 Days)	Second Treatment Visit (7 to 14 days after Visit 2)	Early Termination Visit
Post Instillation Dry Eye Symptoms Assessment		X ^k		X ^k	
Visual Acuity	X				
Biomicroscopy and External Eye Examination	X	X ^l		X ^l	X
Corneal Staining	X				
Conjunctival Staining	X				
TBUT	X				
Intraocular Pressure	X				
Schirmer's Test	X				
Adverse Event Monitoring	X	X		X	X

- a. Prior to conducting study procedures, informed consent will be obtained.
- b. Concomitant medications taken within 28 days of screening will be reviewed
- c. To be completed pre-treatment
- d. Meibomian gland assessment to include clinical exam and meibography
- e. Dry eye symptom questionnaires (OSDI, SPEED, and SANDE with SANDE part 1 at visit 1, 2 and 3 and Part 2 at Visit 2 and Visit 3 only) will be administered pre-dose and before other procedures.
- f. Remove study medication from refrigerator at least 15 minutes before administration
- g. Measurements include: UTMH, LTMH, UTMV, LTMV, and TTMV (UTMV + LTMV)
- h. To be measured three times in one hour (at 0 minutes, 30 minutes, and 60 minute interval)
- i. Timepoints: Pre dose and post dose at 15±5 minutes, 30±10 minutes, 1 hour±20 minutes, 2 hours±30 minutes, 4 hours±30 minutes, and 6 hours±30 minutes
- j. To be completed approximately 5 minutes after dosing
- k. To be completed immediately prior to the 2 hour post dose tear volume measurements
- l. To be completed after 6 hour tear volume assessment

APPENDIX II: ADVERSE EVENT REPORTING

Adverse Event Definitions

Adverse Event (AE): Any untoward medical occurrence in a subject or clinical investigation subject administered a pharmaceutical product; which does not necessarily have a causal relationship with this treatment.

Treatment Emergent Adverse Event (TEAE): A treatment emergent AE (TEAE) is an AE that either commenced following initiation of study treatment or was present prior to study treatment but increased in frequency or severity following initiation of study treatment.

A SERIOUS ADVERSE EVENT (SAE) is any adverse drug experience occurring at any dose that results in any of the following outcomes:

- Death
- A life-threatening adverse drug experience (i.e., the subject is at immediate risk of death at the time of the event)
- In-patient hospitalization or prolongation of existing hospitalization
- A persistent or significant incapacity or substantial disruption of the ability to conduct normal life functions
- A congenital anomaly/birth defect
- Important medical events that may not result in death, be life-threatening, or require hospitalization may be considered serious when, based upon appropriate medical judgment, they may jeopardize the subject and may require medical or surgical intervention to prevent one of the outcomes listed in this definition

A NON-SERIOUS ADVERSE EVENT is any adverse event that does not meet the definitions for serious adverse events as described above.

Adverse Event Classification

Each **Adverse Event** will be classified as **SERIOUS** or **NONSERIOUS** using the definitions provided above.

The **INTENSITY** of each Adverse Event will be classified as **MILD, MODERATE, or SEVERE.**

The **CAUSALITY** of the Adverse Event will be classified as **NOT RELATED to study medication, POSSIBLY RELATED to study medication, or RELATED to study medication defined as follows:**

Not related: An event that does not follow a reasonable temporal sequence from administration to the suspected drug, is not a known response pattern to the suspect drug or due wholly to the subject's clinical state or other factors.

Possibly related: An event that follows a reasonable temporal sequence from administration of the study medication, follows a known or expected response pattern to the suspected drug, but that could be explained by the subject's clinical state or other factors.

Related: An event that follows a distinct temporal sequence from administration of the study medication, follows a known or expected response pattern to the suspected drug, and cannot be explained by subject's clinical state or other factors

Serious Adverse Event Reporting

The following information should be provided when an SAE is reported to Parion Sciences:

1. Protocol Number
2. Site ID
3. Subject Initials
4. Subject Number
5. Subject Demographic information, including:
 - a. Date of Birth
 - b. Sex
 - c. Race
6. Start date of study medication administration
7. Date of last dose of study product
9. SAE information, including:
 - a. SAE Term (diagnosis only; if known or serious signs/symptoms)
 - b. Description of SAE/narrative
 - c. Date of onset
 - d. Outcome
 - e. Date of resolution or death
 - f. Duration of SAE if less than 24 hours
 - g. Relationship to study medication
 - h. Action taken with Study medication
 - i. If ocular, which eye(s) were affected
10. Criteria for classifying the event as serious, including whether the SAE resulted in any of the following:
 - a. Death

- b. Life-threatening
- c. In-patient hospitalization or prolongation of existing hospitalization
- d. A persistent or significant incapacity or substantial disruption of the ability to conduct normal life functions
- e. Congenital anomaly/birth defect
- f. Important medical events that may not result in death, be life-threatening, or require hospitalization may be considered serious when, based upon appropriate medical judgment, they may jeopardize the subject and may require medical or surgical intervention to prevent one of the outcomes listed in this definition. Examples of such medical events include allergic bronchospasm requiring intensive treatment in an emergency room or at home, blood dyscrasias or convulsions that do not result in in-patient hospitalization, or the development of drug dependency or drug abuse.

11. Concomitant medications
12. Relevant history
13. Possible causes of SAE other than study medication
14. Copy of the Adverse Event page from the Case Report Form if the subject has been randomized
15. Signed copy of the SAE form

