6.4 Early Termination Visit

The following assessments will be performed at the Early Termination Visit for randomized subjects who are withdrawn from the study prematurely:

- Assess adverse events since the last visit and during this visit
- Assess concomitant medications and medical changes since last visit
- Collect vital signs (pulse, blood pressure, temperature and respiration rate) and height and weight
- Conduct an abbreviated physical examination (including respiratory, cardiovascular, musculoskeletal, gastrointestinal, and dermatological)
- Conduct a biomicroscopy and external eye examination

6.5 Selecting Dosage Strength in Phase 2

The decision of dose strength for P-321 Ophthalmic Solution in Phase 2 of the study will be the responsibility of the Data Review Group constituted by the Principal Investigator (or a designee not directly involved in the conduct of the study), the Medical Monitor and representatives of Parion Sciences. Decision on the dose level to be given in Phase 2 will be made based on unmasked review of the study data from the first 8 subjects by the review committee. Data to be considered will include safety and efficacy measures. A detailed criterion for Dose selection for Phase 2 is described in [Appendix XIV](#) and outlined below.

The dose level may be increased to 0.05% in Phase 2 in the event that:

- 1) No cases of serious, suspected related, unexpected events are noted in Phase 1 OR
- 2) No cases of serious ocular safety events are noted in Phase 1
- 3) Lack of evidence that P-321 produced an increase in tear volume based on OCT and/or Keratograph 5M, or evidence that additional improvements in tear volume (or the duration of effect) may be obtained with a higher dose.

The dose level may be decreased to 0.01% in Phase 2 in the event that:

- 1) No cases of serious, suspected related, unexpected events are noted in Phase 1
- 2) No cases of serious ocular safety events are noted in Phase 1
- 3) There is evidence of a significant increase in tear volume and the duration of effect based on OCT and/or Keratograph 5M

The dose level may remain at 0.017% (the same as in Phase 1) in the event:

- 1) No cases of serious, suspected related, unexpected events are noted in Phase 1
- 2) No cases of serious ocular safety events are noted in Phase 1
- 3) There is not compelling data to either increase or decrease the strength for Phase 2.

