7.7 Maintenance of Randomization and Procedure for Breaking the Code

The treatment assignments will be masked to the investigator, medical monitor, study site personnel, subjects in the study and those involved in the conduct of the study.

Only in the case of a medical emergency, or occurrence of a suspected related, unexpected, SAE, may the randomization code be unmasked and made available to the investigator, medical monitor, subject, and/or other personnel involved in the monitoring or conduct of this study. In the absence of medical need, the randomization code will not be available to the above personnel until after the study is completed and the database is locked.

The Data Review Group will review unmasked data. The Medical Monitor and Principal Investigator (or designee) and members of the Parion team not involved in the conduct of the study will be unmasked as part of the Data Review Group for decision making on the strength of P-321 Ophthalmic Solution to be used in Phase 2 of the study. The treatment assignments will remain masked to subjects in the study, the clinical monitor, and other site and Parion Sciences personnel involved in the conduct of the study and not involved in the Data Review Group. Additional unmasked reviews of subject data may occur throughout the study to make recommendations on further dose adjustments and for planning purposes. These reviews will follow the procedures outlined in [Section 6.5](#).

For Phase 1, a randomization list will be generated and the kits will be labeled in a masked fashion. The randomization assignments will be kept in a secure area at Parion Sciences, Inc. or designee. For Phase 2, a randomization list will be provided to the pharmacy and the pharmacy will distribute the assigned drug according to the randomization schedule with subjects remaining masked.

In case of a medical need, the investigator will treat the subject as needed regardless of randomized treatment. Since there is no specific antidote to P-321 Ophthalmic Solution, immediate emergency unmasking is not necessary. If the investigator feels it is necessary to unmask a subject's treatment assignment after an emergency situation, the investigator must call the medical monitor and notify Parion Sciences, Inc. The treatment assignment will be revealed on a subject-by-subject basis, leaving the masking of the remaining subjects intact.

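### Appendix II allows no reaction with a wholly new pattern to be graded possibly related or related, which largely empties the condition on serious, suspected related, unexpected events used for dose selection and unmasking

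*Combined protocol and SAP*

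**What the plan says.** Appendix II, under Adverse Event Classification, gives the only causality scale in the protocol. It has three grades: "NOT RELATED to study medication, POSSIBLY RELATED to study medication, or RELATED to study medication defined as follows". In outline:

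- **Not related**: the timing is not reasonable, or the event "is not a known response pattern to the suspect drug or due wholly to the subject's clinical state or other factors". The grounds form a comma list that ends in an or.
- **Possibly related**: the timing is reasonable, and the event "follows a known or expected response pattern to the suspected drug, but that could be explained by" other causes.
- **Related**: the timing is distinct, and the event "follows a known or expected response pattern to the suspected drug, and cannot be explained by" other causes.

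Three other places rely on a causality judgement:

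- Section 6.5 and Appendix XIV list the same safety condition for raising, lowering and keeping the dose: "No cases of serious, suspected related, unexpected events are noted in Phase 1".
- Section 7.7 allows the code to be broken in a medical emergency or on "occurrence of a suspected related, unexpected, SAE, may the randomization code be unmasked".
- Section 8.1.4 plans a table of adverse events by relationship to study medication.

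Suspected related is not one of the three grades. Neither it nor unexpected is defined. The file holds two versions of the protocol, and these passages carry the same conditions and grades in both.

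**The concern.** A causality scale should let an investigator say that a new kind of reaction was probably caused by the drug. Here the pattern requirement mixes two questions that are normally kept apart: whether the drug caused the event, and whether such an event was already known. Sections 6.5 and 7.7 and Appendix XIV then ask for events that are both suspected related and unexpected, a combination that the scale hardly permits.

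The condition matters because it stands in all three dose paths. Under Appendix XIV, if it failed, the only listed recommendations left would be to discontinue the study or amend the protocol. A condition that can hardly fail cannot do that work.

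Little is known about this drug in humans, so a new pattern is a realistic case. Section 2.3 reports one completed study, with 40 treated subjects and strengths up to 0.01%, and no clinically relevant drug-related effects on safety measures. This trial starts at 0.017% and may use 0.05%, which is 0.05 / 0.01 = 5 times the highest strength in that study.

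**Working it through.** The plan gives no figure to reproduce. The check applies the Appendix II definitions to every type of event.

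**1. Inputs.** From Appendix II: timing (fits or does not), pattern (known, expected, or neither), and alternative explanation (accounts for the event wholly, could account for it, cannot account for it). Appendix II asks for reasonable timing in one grade and distinct timing in another. I treat both as fitting, because the difference cannot help an event that fails on pattern.

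**2. Two readings of Not related.** Reading A: any one ground is enough. Reading B: the first two grounds (timing and pattern) must hold together, while a whole alternative explanation is enough alone.

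**3. A wholly new pattern, neither known nor expected.** There are 2 × 3 = 6 combinations.

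| Timing fits | Alternative explanation | Reading A | Reading B |
|---|---|---|---|
| Yes | Wholly | Not related | Not related |
| Yes | Could | Not related | No grade |
| Yes | Cannot | Not related | No grade |
| No | Wholly | Not related | Not related |
| No | Could | Not related | Not related |
| No | Cannot | Not related | Not related |

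Reading A gives 6 Not related and 0 related grades. Reading B gives 4 Not related, 2 without any grade, and 0 related grades. The two combinations without a grade are the ones that matter most: fitting timing and no full alternative explanation.

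**4. A known pattern that is nevertheless unexpected.** There are again 6 combinations. The 3 with fitting timing can receive a related grade under both readings: 2 possibly related (wholly, could) and 1 related (cannot). The wholly explained one also meets Not related, so 2 of the 3 are unambiguous. This is the only way for an event to be both related and unexpected.

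**5. Against the dose conditions and Section 7.7.** Take suspected related to mean possibly related or related. A serious event with a wholly new pattern then never counts against the dose condition and never opens that unmasking ground. In the relationship table it appears under Not related (reading A) or has no proper row (reading B, where timing fits and the event is not wholly explained).

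**6. Section 6.5 against Appendix XIV.** For a dose increase, Section 6.5 joins this condition to the one on serious ocular events with OR, and Appendix XIV joins them with AND. Where the first condition is met because of the scale, the OR is satisfied whatever happens to the second. Under AND the ocular condition still binds.

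**The case against.** The strongest reply is that the two key terms are undefined and that a known pattern is enough for a related grade. Section 2.2.3 describes dose-dependent ocular irritation in animals, minimal or slight. Section 6.6 names hyperkalemia as a previous potential concern, with no potassium changes in the first clinical study. A serious form of either might be graded related and still be judged unexpected. That stands: a reader might infer that the combination is impossible by definition, but step 4 shows a route to it, and the Investigator Brochure that could settle expectedness is not among the documents.

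A reader might also infer that every new reaction is forced into Not related. That holds on reading A only. On reading B the scale has a gap instead.

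Third, the plan has safeguards that need no causality grade:

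- Serious ocular events are a separate condition in all three dose paths, subject to the OR/AND conflict for an increase.
- The Data Review Group sees adverse events unmasked, may request more unmasked data for safety, and may recommend discontinuing or amending (Appendix XIV).
- Serious events go to the sponsor within 24 hours whatever their cause (Section 10.3), and the trial may be stopped for a significant number of similar adverse events (Sections 5.5 and 8.5).
- A medical emergency still permits unmasking (Section 7.7).
- Adverse events are also tabulated by treatment group, sequence and severity (Section 8.1.4), so a new reaction would still show in the comparison with placebo.

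These points stand and limit the harm. They do not make the written condition work. Several rest on judgement, and the ocular condition does not cover a serious new event outside the eye.

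**Conclusion.** The point holds in this form: a reaction with a wholly new pattern cannot be graded possibly related or related on either reading of Appendix II (0 of 6 combinations). That conflicts with Sections 6.5 and 7.7 and Appendix XIV.

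The further conclusion, that the dose condition and one unmasking ground are largely emptied, rests on two assumptions: that suspected related means the upper two grades, and that unexpected usually means a pattern not seen before. Both are natural, but neither is written down. The documents do not support the inference that dose selection has no working safety condition, given the ocular condition and the unmasked review.

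This should be fixed before causality grades feed the Phase 1 data review. Because of the other safeguards, it does not by itself undermine the trial.

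**What to change.** 1. In Appendix II, remove the known or expected pattern as a required element of Possibly related and Related, and remove its absence as a ground for Not related. Grade on timing and alternative explanation, with a known pattern as supporting evidence only.
2. Word the grades so that every combination fits exactly one. Deleting the pattern clauses alone would still leave an event with reasonable but not distinct timing and no other explanation without a grade.
3. Judge expectedness as a separate item against the Investigator Brochure, which Section 13.1 already mentions. Define unexpected, and state which grades count as suspected related.
4. Reconcile Appendix II with Sections 6.5 and 7.7 and Appendix XIV, including the OR in Section 6.5 against the AND in Appendix XIV. Which dose rule is right is for the sponsor to settle. This review takes no position on it.

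The cost is a change of wording in the protocol and in the instructions for the adverse event form. The small downside is that somewhat more events may be graded possibly related.
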